of patients who otherwise would not benefit due to the early administration requirement for tranexamic acid. The results provided by the successful completion of this proposal will have paramount implications for both civilian and military injured patients as control of coagulopathy and hemorrhage and delay to definitive care represent major impediments. The current proposal will add needed understanding and insight into improving outcomes when these impediments exist and will promote focus on the mechanisms responsible and the dosing requirements of tranexamic acid that maximize its benefit.

CLINICAL PROTOCOL

A. Statement of Work

Principal Investigators (PIs): [name] and [name] will oversee all planning and execution of the Study of Tranexamic acid during Air Medical Prehospital transport (STAAMP) trial which is a 3 year, multi-center, randomized, double blinded, placebo controlled clinical trial. For patients at risk of bleeding who are transported by emergency medical transport, a 1 gram bolus of prehospital tranexamic acid and subsequent in hospital tranexamic acid dosing regimens will be compared to placebo for clinical, coagulation, inflammatory and dosing regimen endpoints.

Coordinating Center: The University of Pittsburgh will be both the clinical outcome and data coordinating center. The University of Pittsburgh under the auspices of the Principal Investigators will be responsible for the education and training of participating center research staff and will oversee education and training of prehospital providers and research staff for participating centers. The University of Pittsburgh under the auspices of the Principal Investigators will be responsible for sample acquisition, sample storage, data acquisition and entry via web based platform, and maintenance of data integrity.

Participating Centers: Site Investigators from participating centers will oversee the planning and execution of the trial at their respective centers.

The Principal Investigators, the University of Pittsburgh and participating centers will thru the execution of the trial:

1. Determine whether prehospital tranexamic acid as compared to placebo reduces 30 day mortality, reduces the incidence of hyperfibrinolysis, Acute Traumatic Coagulopathy and improves early markers of coagulopathy and hyperfibrinolysis. (r-TEG parameters, D-dimers, activated protein C, and plasmin-anti-plasmin complexes)

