Secondary Hypothesis 3B: Prehospital tranexamic acid as compared to placebo will attenuate trauma-induced pro-inflammatory changes and immunosuppression by reducing the early inflammatory cytokine response (GM-CSF, IFN- γ , IL-1 β , IL-2, IL-4, IL-5, IL-6, IL-8, IL-10 and TNF- α), HMGB1 levels and early inflammatory gene responses as measured by RT-PCR.

E.3.4. Secondary Aim#4: Determine whether different dosing regimens of tranexamic acid upon arrival in the hospital are associated with improvements in hyperfibrinolysis, markers of coagulopathy, clinical outcomes, platelet and leukocyte activation and the early inflammatory response.

Secondary Hypothesis 4A: Repeat dosing of 1 gram of tranexamic acid followed by 1 gram over approximately 8 hours after hospital arrival in patients who have already received 1 gram of prehospital tranexamic acid will lower the incidence of 12 hour (from arrival) hyperfibrinolysis (estimated percent lysis > 7.5%), coagulopathy (INR > 1.4) and improve r-TEG markers of coagulopathy, D-dimer levels, activated protein C levels and plasmin-antiplasmin complex levels as compared to standard dosing of tranexamic acid (1 gram over approximately 8 hours) or abbreviated dosing (no additional tranexamic acid).

Secondary Hypothesis 4B: Repeat dosing of 1 gram of tranexamic acid followed by 1 gram over approximately 8 hours after hospital arrival in patients who already received prehospital tranexamic acid will lower the incidence of 24 hour and 30 day mortality, acute lung injury, multiple organ failure and nosocomial infection as compared to standard dosing or abbreviated dosing.

Secondary Hypothesis 4C: Repeat dosing of 1 gram of tranexamic acid followed by 1 gram over approximately 8 hours after hospital arrival in patients who already received prehospital tranexamic acid will reduce 12 hour (from arrival) base deficit, 24 hour crystalloid requirements and 6 hour and 24 hour blood and blood component transfusion requirements (PRBC, FFP and platelets) as compared to standard dosing or abbreviated dosing.

Secondary Hypothesis 4D: Repeat dosing of 1 gram of tranexamic acid followed by 1 gram over approximately 8 hours after hospital arrival in patients who already received prehospital tranexamic acid will reduce 12 hour and 24 hour (from arrival) markers for platelet and leukocyte activation, plasmin

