H.3.1. Prehospital Phase Intervention: Once inclusion and exclusion are verified while the patient is being transported via emergency medical transport to a STAAMP trial participating center, in a randomized, double blinded fashion, either 1 gram bolus of tranexamic acid diluted in 100cc of normal saline (pre-prepared on emergency vehicle) or placebo of identical volume will be infused intravenously or intraosseously (if IO access was obtained due to a clinical need per standard of care) into the patient over approximately 10 minutes (“Bag A”). After receiving the prehospital phase intervention, standard operating procedures utilizing goal directed crystalloid infusion will be followed (see **H.7. Prehospital Standard Operating Procedures** below)

H.3.2. In-hospital Phase Intervention: Upon arrival, patient blood and labs will be sampled and arrival rapid-TEG analysis will be performed within first 6 hours. After inclusion and exclusion criteria verification by research staff, in a double blinded, randomized fashion, those patients who received tranexamic acid in the prehospital phase will receive 1 of 3 different dosage regimens:

1. Standard Tranexamic acid Dosing: 1 gram infusion over approximately 8 hours
2. Repeat Tranexamic acid Dosing: 1 gram bolus **and** 1 gram infusion over approximately 8 hours
3. Abbreviated Tranexamic acid Dosing: No further tranexamic acid to be given

For intervention blinding purposes, each patient will receive both a bolus dose (either tranexamic acid or placebo), “Bag B,” and 8 hour infusion (either tranexamic acid or placebo), “Bag C,” depending on the randomized dosing regimen. (Figure 13. below)

H.3.2.1 Adjustment For Renal Insufficiency: Subjects with a known or suspected history of renal insufficiency will receive a renal dose adjustment for the 8 hour repeat infusion (Bag C). The Estimated Body Weight Table will be used to determine the dose (Figure 12). The dose will be capped at 1000 mg.

1. Standard Dosing: bolus- no dose adjustment / infusion- 1.25 mg/kg/hr x 8hrs
2. Repeat Dosing: bolus- no dose adjustment / infusion- 1.25 mg/kg/hr x 8hrs
3. Abbreviated Dosing: bolus- no dose adjustment / infusion- 1.25 mg/kg/hr x 8hrs

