H.5.2. *In-hospital Phase Allocation:* Using a web based, randomization assignment program built specifically for the trial, research staff will provide and input the prehospital intervention box # and treatment pack # into the web based platform at each site and be provided the In-hospital treatment allocation to be utilized for the second phase intervention. IDS at the University of Pittsburgh and each respective pharmacy at the participating sites will be provided with the random allocation sequence and will be unblinded to the in-hospital allocation assignment. The accepting research staff and pharmacy will verify they have the same in-hospital phase treatment assignment as an additional check to the allocation assignment. An allocation sequence based upon a block size of 9 again generated with a computer random number generator will be utilized for those who received prehospital Tranexamic Acid. Each respective IDS or pharmacy will prepare the in-hospital phase treatment (approximate 10 minute and 8 hour infusion). The patient and all treatment and research staff will be blinded to the treatment that is received.

H.6. Blinding: The trial is a double blinded trial for both the prehospital phase and in-hospital phase interventions. The participants, investigators, research coordinators and staff, and persons having any contact with the patients will be blinded to study treatment assignments. The IDS at the University of Pittsburgh will be unblinded to the prehospital phase treatment arm and the respective pharmacy at each center will be unblinded once the treatment prehospital treatment information is provided to them by research staff. Both IDS at the University of Pittsburgh and the respective IDS or pharmacy at each center will be unblinded to the in hospital treatment assignment.

H.7. Prehospital Standard Operating Procedures: To minimize over exuberant crystalloid resuscitation during the prehospital phase of treatment after enrollment, further crystalloid resuscitation post-intervention will follow a 'goal directed' standard operating procedure (SOP). Crystalloid infusion following the intervention will be based upon hemodynamic status (SBP < 90mmHg) with infusion of 500cc boluses of crystalloid for those patients with persistent hypotension. Normotensive patients will receive crystalloid infusion at maintenance rate. (Figure 13. above) All crystalloid volumes will be monitored relative to transport time for all

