
J.2. Analysis of Prehospital Randomized Secondary Outcomes: Unless there is sufficient power (predetermined before the analysis is begun), the approach to analysis of secondary endpoints will generally be calculation of confidence limits on intervention group differences or model parameters rather than formal tests of significance at a specified critical level as the trial will not have sufficient power to detect difference in all of these outcomes. However, these comparisons will add to the knowledge of the benefits and risks of the interventions. Parametric and nonparametric comparisons will be applied according to normalcy. All tests used will be two-tailed tests at significance level (α) of 0.05. For prehospital randomized clinical outcomes we will use Chi-square with 95% confidence intervals for dichotomous outcomes and parametric or non-parametric testing for continuous variable with 95% confidence intervals. For prehospital randomized laboratory or exploratory outcomes we will use parametric or non-parametric testing for continuous variable with 95% confidence intervals.

J.3. Analysis for Second Stage In-hospital Randomized Dosage Regimens: Chi-square test will be able to test the effect of different tranexamic dosage regimens on hyperfibrinolysis. Similarly, chi-square will be used to detect any differences between dosage groups for 30 day mortality. To detect a trend in dosage response, test for trend will be implemented. As additional analysis and to account for site and to adjust for some important covariates, we will use logistic regression to test the effect of dosage on hyperfibrinolysis. Similarly Cox proportional hazards regression can be used for 30 day mortality. *For In-hospital randomized dosage regimen comparison for clinical outcomes* we will use Chi-square with 95% confidence intervals for dichotomous outcomes and parametric or non-parametric testing for continuous variable with 95% confidence intervals. *For In-hospital randomized dosage regimen comparison for laboratory or exploratory outcomes* we will use parametric or non-parametric testing for continuous variable with 95% confidence intervals.

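### J.3 tests the dosing regimens with a chi-square for any difference and a trend test, neither of which isolates repeat versus standard dosing, the superiority that Hypotheses 4A to 4D assert

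*Combined protocol and SAP*

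**What the plan says.** The hypotheses under Secondary Aim 4 (section E.3.4) have a direction and a named winner. Each of 4A to 4D predicts that repeat dosing gives better results than the other two regimens. In 4B, for example, the prediction covers mortality, lung injury, "multiple organ failure and nosocomial infection as compared to standard dosing or abbreviated dosing".

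Under H.3.2, "those patients who received tranexamic acid in the prehospital phase will receive 1 of 3 different dosage regimens". H.5.2 describes the allocation: "An allocation sequence based upon a block size of 9 again generated with a computer random number generator". The ratio is not stated; a block of 9 for three regimens suggests 1:1:1.

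The analysis is in J.3:

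- Hyperfibrinolysis: "Chi-square test will be able to test the effect of different tranexamic dosage regimens on hyperfibrinolysis".
- 30-day mortality: "Similarly, chi-square will be used to detect any differences between dosage groups for 30 day mortality".
- Dose response: "To detect a trend in dosage response, test for trend will be implemented".
- Additional analyses with site and covariates: "we will use logistic regression to test the effect of dosage on hyperfibrinolysis", and optionally a Cox model for mortality.
- Other outcomes: chi-square with 95% confidence intervals for dichotomous outcomes, and parametric or non-parametric tests with 95% confidence intervals for continuous ones.

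J.3 does not say which pair of regimens any interval or model coefficient refers to, which regimen is the reference, in what order the tests are read, or what result would count as repeat dosing being better. It states no significance level; J.2 gives two-sided 0.05. Section K contains no power calculation for the regimen comparison.

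**The concern.** A three-group chi-square asks whether the three rates are all equal. A trend test asks whether the rate falls as dose rises. Hypotheses 4A to 4D ask whether repeat dosing beats standard dosing and whether it beats abbreviated dosing. If abbreviated dosing is worse and the other two regimens are alike, both named tests tend to reject, while the statement that repeat beats standard is false.

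The synopsis lists determining the optimal dosing among the trial's aims. If the plan is followed as written, a significant J.3 result does not say which regimen differs from which. The contrast that would settle it is left to be chosen after the data are seen.

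**Working it through.** **The plan's own power figures.** Only the primary comparison has any (K.1: 497 per arm, 16% control mortality, pooled-variance Z test). For 9.65% v 16%, the pooled rate is 0.12825 and z = [0.0635 × √497 − 1.96 × √(2 × 0.12825 × 0.87175)] / √(0.0965 × 0.9035 + 0.16 × 0.84) = (1.416 − 0.927) / 0.471 = 1.04, so power is 0.85. The other two rows give 0.9001 and 0.7996. The table reproduces, but it does not bear on J.3.

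**Inputs for the regimen comparison**

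- Patients per regimen: 497 / 3 ≈ 166. This assumes equal allocation and that every tranexamic acid patient reaches the second stage, so it is an upper figure.
- Rates of 10% and 16% come from P.4. All other rates (8%, 12%, 14%, 20%, 5%) are assumptions.
- Two-sided 0.05 is carried over from J.2.
- Trend scores are assumed to be 0, 1, 2 for abbreviated, standard and repeat, which match the grams given in hospital without renal adjustment.

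**Test statistics with n per regimen**, where p̄ is the overall rate:

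- Chi-square, 2 df: n × Σ(pᵢ − p̄)² / [p̄(1 − p̄)].
- Trend: z = (p_repeat − p_abbreviated) / √[p̄(1 − p̄) × 2/n].

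With equal groups and equally spaced scores, the standard regimen drops out of the trend numerator. It enters only through p̄, so this statistic does not compare repeat with standard.

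**Simulation** (binomial, 166 per regimen, one million trials per row):

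| Mortality, abbreviated / standard / repeat | Chi-square significant | Trend significant, favouring more drug | Repeat significantly better than standard (pairwise z) |
|---|---|---|---|
| 14 / 10 / 10% | 20% | 21% | 2.6% |
| 16 / 10 / 10% | 39% | 39% | 2.6% |
| 16 / 8 / 8% | 66% | 65% | 2.5% |
| 20 / 8 / 12% | 84% | 57% | 0.1% |

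In the first three rows repeat has no advantage over standard, and a direct contrast would wrongly favour it in about 2.5% of trials. In the last row repeat is truly worse than standard, yet the trend points to more drug in more than half of trials.

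**One data set.** Take 30, 13 and 15 deaths of 166 each, so p̄ = 58/498 = 0.1165.

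- Chi-square = 10.11, p = 0.006.
- Trend z = (15 − 30)/166 / √(0.1029 × 2/166) = −0.0904 / 0.0352 = −2.57, p = 0.010.
- Repeat minus standard = 2/166 = +1.2 points (95% CI −4.8 to +7.2).

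Both named tests are significant and the point estimate for repeat v standard is in the wrong direction.

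**Two tests of one question.** With 10% mortality in every regimen, each named test rejects in about 4.9% of trials and at least one rejects in about 7.4%.

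**What the direct contrast can deliver.** At 10% in both regimens the 95% half-width is 1.96 × √(2 × 0.10 × 0.90 / 166) = 6.5 points. Power for 5% v 10% is 41%; 80% power would need about 435 per regimen.

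**The case against.** The strongest reply is that J.3 does more than test. It promises 95% confidence intervals and adds regression models, and either could supply repeat v standard. J.2 also prefers confidence limits to formal tests for underpowered secondary outcomes. This softens the point but does not remove it. J.3 does not say whether its intervals are per regimen or on differences, or between which regimens; the models have no stated dose coding or reference. J.2 is headed for the prehospital comparison. J.3 also never says that the chi-square is a single three-group table; that is inferred from three regimens and a test of any difference.

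Aim 4 itself is worded loosely: it asks whether regimens are associated with improvements, which a global or trend test partly answers. That is fair, but Hypotheses 4A to 4D are specific.

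Three stronger readings are tempting and the documents do not support them.

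- *The plan will declare repeat dosing superior on a significant chi-square or trend.* No section says so. The plan leaves the inference open; it does not prescribe the wrong one.
- *Error inflation is larger, because pairwise tests at 0.05 would be added.* J.3 lists no pairwise tests. The two it names give about 7.4%.
- *J.3 omits a promised comparison of each regimen with placebo.* The Statement of Work says that "subsequent in hospital tranexamic acid dosing regimens will be compared to placebo for clinical, coagulation, inflammatory and dosing regimen endpoints", but the subject of that sentence also includes the prehospital bolus, so it can mean the whole tranexamic acid strategy. Item 4 of the same list and Hypotheses 4A to 4D compare regimens only with one another. Regimen groups are also formed after arrival and eligibility verification, so setting them against all placebo patients would compare groups formed at different times.

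**Conclusion.** The point holds. The two tests named in J.3 do not test the superiority stated in Hypotheses 4A to 4D, and the items that could do so have no named contrast. With repeat equal to standard, the chi-square is significant in about 20% to 66% of trials and the trend test in about 21% to 65%, as the shortfall of abbreviated dosing goes from 4 to 8 points. At the plan's own 10% and 16% both figures are about 39%. These percentages depend on the assumed rates, equal allocation, trend scores and 0.05 level; the logical gap does not.

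The consequence is limited to the interpretation of secondary Aim 4. The primary 30-day mortality comparison, its sample size and its stopping boundaries are unaffected. The regimen comparison is unpowered however it is tested, which is a further reason to report differences with intervals. It should be corrected before the regimen data are unblinded for analysis.

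**What to change.** In J.3:

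1. Name repeat v standard and repeat v abbreviated as the contrasts that test Hypotheses 4A to 4D.
2. Report each difference with a 95% confidence interval for every outcome type: dichotomous, continuous and time to event.
3. Use the same two contrasts in the logistic and Cox models, with dose entered as a three-level factor.
4. State that repeat dosing is called better than a comparator only on the contrast with that comparator.
5. Label the three-group chi-square and the trend test as supportive, and state the trend scores.
6. State the significance level for J.3 and whether any multiplicity rule applies.

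For item 6, a closed test is one option: the global test at 0.05 first, then the pairs at 0.05. With three regimens it controls error across the three pairs (any pairwise claim in about 4.9% of trials at 10% in every regimen), but only within one outcome, and Aim 4 has many. Its price should be stated: at 10/10/5%, power for repeat v standard falls from about 41% to 30%.

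The cost is a paragraph in J.3 and a few table columns. No change to enrolment, treatment, data collection or the primary analysis is needed.
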